5.5.2. Montgomery-Asberg Depression Rating Scale (MADRS)

Definitions

The MADRS is a clinician-rated scale designed to measure depression severity and to detect changes due to antidepressant treatment. The scale consists of 10 items, each of which is scored from 0 (item is not present or is normal) to 6 (severe or continuous presence of the symptoms), for a total possible score of 60. Higher scores represent a more severe condition. The MADRS evaluates apparent sadness, reported sadness, inner tension, sleep, appetite, concentration, lassitude, interest level, pessimistic thoughts, and suicidal thoughts. The test exhibits high inter-rater reliability.

If 2 or more items are missing, no imputation will be performed, and the total score will be left missing. Otherwise, the total score will be calculated as sum of the non-missing items multiplied by the ratio of the maximum number of items (i.e., 10) to the number of non-missing items.

A subject is defined as a responder at a given time point if the percent improvement in MADRS total score from baseline is \geq 50% or if the MADRS total score is \leq 10.

A subject is defined as being in remission at a given time point if the MADRS total score is ≤ 10 .

Rating of the MADRS will be conducted face-to-face with the participants by an independent rater. However, there may be situations where the rating is done remotely. The proportion of ratings by type of contact (site visit, home visit, remote video call) will be summarized by visit and study intervention.

Analysis Methods

See section 5.5.1 for the analysis of the MADRS total score.

The proportion of subjects who responded and who are in remission will be summarized for each scheduled visit with N and % in each category by study intervention. Summaries of both observed and LOCF data will be presented. Stacked bar graphs will be made to show the proportion of subjects who are in remission and who responded but not in remission over time. In a sensitivity analysis, the proportions will be calculated with observed data in the numerator and the full analysis set in the denominator.

5.5.3. Relapse

Definitions

The definition of relapse is described in section 5.4.1.1.

The remission time point is the first time point at which the participant is in remission. The time to first relapse will be calculated from the remission time point until the date of first relapse.

Analysis Methods

This analysis will only include participants for whom the remission time point is before or at Week 8. The number of patients with a relapse and the reason(s) for relapse, being 'MADRS total score ≥ 22 for 2 assessments separated by 5 to 15 days'; 'subject been hospitalized for worsening of depression, or for suicide prevention or due to a suicide attempt'; 'Has there been a suicide attempt, completed suicide or any other clinically relevant event determined per the investigator's clinical judgement to be indicative of a relapse of depressive illness, but for which the participant was not hospitalized', will be summarized with N and % in each category by study intervention.

The time to first relapse will be summarized with descriptive statistics (N, mean, standard deviation [SD], median and range [minimum and maximum]). Time to first relapse (from remission time point) will be analyzed by the Kaplan-Meier method. Time to relapse will be summarized with median, 25th and 75th percentile (if estimable). Confidence intervals of 25th, 50th, and 75th percentile of time to relapse will also be provided.

The relapse narratives will be listed.

5.5.4. Clinical Global Impression – Severity (CGI-S)

Definitions

The CGI-S evaluates the severity of psychopathology on a scale of 1 to 7. Considering total clinical experience, a subject is assessed on severity of mental illness at the time of rating according to: 1 = normal (not at all ill); 2 = borderline mentally ill; 3 = mildly ill; 4 = moderately ill; 5 = markedly ill; 6 = severely ill; 7 = among the most extremely ill patients.

Analysis Methods

See section 5.5.1 for the analysis of the CGI-S score.

In addition, a frequency distribution will be provided for each scheduled visit. Summaries of both observed and LOCF data will be presented.

5.5.5. Clinical Global Impression – Change (CGI-C)

Definitions

The CGI-C evaluates the total improvement whether or not due entirely to drug treatment on a scale of 1 to 7. Compared to the condition at baseline, a subject is assessed on how much he/she has changed, according to: 1 = very much improved; 2 = much improved; 3 = minimally improved; 4 = no change; 5 = minimally worse; 6 = much worse; 7 = very much worse.

Analysis Methods

A frequency distribution will be provided for each scheduled visit. Summaries of both observed and LOCF data will be presented.

5.5.6. Therapeutic benefit assessment (esketamine arm)

Definitions

The therapeutic benefit assessment at visit week 4 for the esketamine receiving subjects consists of 3 Yes/No questions: "Did the evaluation of therapeutic benefit take place?", "Was there evidence of therapeutic benefit?" and "Was the treatment with esketamine continued?". If there was no evidence of therapeutic benefit *and* the treatment with esketamine continued, the reason is reported as: "Longer time to response / remission expected", "Negative life event / unstable life circumstances", "Other".

Analysis Methods

A frequency distribution will be provided for each question. The specifications of reason "Other" will be listed.

5.5.7. Treatment Continuation Assessment

Definitions

The treatment continuation assessment is scheduled for every 4 weeks starting as of visit week 8. The treatment decision is based on the CGI-C value of the visit, and is recorded as "Study intervention continued", "Study intervention not continued and switch to alternative SoC". The reason for continuation of study intervention in case of CGI-C >4 at 2 consecutive visits is recorded as: "Patient's preference", "Longer time to response/remission is expected", "Negative life event/unstable life circumstances", "Lack of alternative treatment option", "Other".

Analysis Methods

A frequency distribution will be provided for each question for each scheduled visit. The specifications of reason "Other" will be listed.

5.5.8. Patient Health Questionnaire – 9 item (PHQ-9)

Definitions

The PHQ-9 is a validated 9-item, PRO measure to assess depressive symptoms. Each item is rated on a 4-point scale (0=not at all, 1=several days, 2=more than half the days, and 3=nearly every day). The participant's item responses are summed to provide a total score (range of 0 to 27), with higher scores indicating greater severity of depressive symptoms. In addition, the question "If you checked off any problems, how difficult have these problems made it for you to do your work, take care of things at home, or get along with other people?" is scored as "Not difficult at all", "Somewhat difficult", "Very difficult", "Extremely difficult".

A subject is defined as a responder at a given time point if the percent improvement from baseline in PHQ-9 total score is \geq 50%.

A subject is defined as a remitter at a given time point if the PHQ-9 total score is \leq 9 at that time point.

Analysis Methods

See section 5.5.1 for the analysis of the PHQ-9 total score.

Frequency distributions will be provided for the addition question on the PHQ-9, PHQ-9 response and PHQ-9 remission for each scheduled visit. Summaries of both observed and LOCF data will be presented.

5.5.9. Quality of Life in Depression Scale (QLDS)

Definitions

The QLDS is a disease-specific validated PRO measure which assesses the impact that depression has on a participant's quality of life. It is a 34-item self-rated questionnaire which consists of dichotomous response questions, with the response being either True/Not True. Each statement on the QLDS is given a score of "1" or "0". A score of "1" is indicative of adverse quality of life. All item scores are summed to give a total score that ranges from 0 (good quality of life) to 34 (very poor quality of life). As the measure contains positive as well as negative items, item scores are not always in the same order - that is, not all 'true' responses are allocated a score of "1". Listed below are the statements with the alternative responses and their associated scores:

Liust want time to pass	True	1	
T Just want time to puss	Not true	0	
I feel hopeful about the future	True	0	
i ior noperar about the ratare	Not true	1	
I find it hard to hold a conversation	True	1	
	Not true	0	
I like to know what is going on in the world	True	0	
	Not true	1	
I feel as if my life is wasting away	True	1	
reer us it ing inte is wasting away	Not true	0	
I feel as if I am not in control of my life	True	1	
	Not true	0	
I am reluctant to leave the house	True	1	
	Not true	0	
On the whole, Leniov the things I do	True	0	
on the whole, renjey the timigs rule	Not true	1	
I have lost all pleasure in life	True	1	
Thave lost an pleasure in me	Not true	0	
I feel as if I have nothing to offer anyone	True	1	
	Not true	0	
I turn away from people I care about	True	1	
	Not true	0	
I take good care of myself	True	0	
	Not true	1	
I am able to think about the future	True	0	
	Not true	1	
I just want to hide away	True	1	
L Just mart to mas a may	Not true	0	
I look forward to things	True	0	
	Not true	1	
I've forgotten what it's like to enjoy myself	True	1	
r to rotgotten what it is into to onjoj mjoon	Not true	0	

I can't be bothered with my friends	True	1	
	Not true	0	
I can cope easily with everyday tasks	True	0	
	Not true	1	
I cut myself off from other people	True	1	
5 1 1	Not true	0	
It is difficult for me to make even simple decisions	True	1	
	Not true	0	
I feel as if I am a burden to people	True	1	
	Not true	0	
Most of the time I just sit and stare into space	True	1	
	Not true	0	
I can't face anyone	True	1	
	Not true	0	
I shut everything out	True	1	
	Not true	0	
I'm neglecting my appearance	True	1	
	Not true	0	
I can see the funny side of things	True	0	
, ,	Not true	1	
I don't take in what people say to me	True	1	
1 1 5	Not true	0	
I feel as if I'm letting everyone down	True	1	
	Not true	0	
I dread each coming day	True	1	
	Not true	0	
I enjoy my food	True	0	
	Not true	1	
I avoid people if I can	True	1	
1 1	Not true	0	
I am reluctant to answer the door or the telephone	True	1	
1	Not true	0	
My life has no meaning	True	1	
	Not true	0	
I am able to cope with everyday problems	True	0	
1 J J F	Not true	1	

In case there are missing items, it is recommended that for respondents with between one and six missing responses (that is, cases with less than 20% missing data), the total score is calculated as follows:

T = x / (34 - m) * 34

where T is the final total score, x is the item summation score, m is the number of missing items. Cases with more than six missing responses cannot be allocated a total score.

Analysis Methods

See section 5.5.1 for the analysis of the QLDS total score.

5.5.10. European Quality of Life Group, 5-Dimension, 5-Level (EQ-5D-5L)

Definitions

The EQ-5D-5L is a validated standardized instrument for use as a measure of health outcome, primarily designed for self-completion by respondents. It consists of the EQ-5D-5L descriptive system and a visual analogue scale (EQ-VAS).

The EQ-5D-5L descriptive system comprises the following 5 dimensions: mobility, self-care, usual activities, pain/discomfort and anxiety/depression. Each of the 5 dimensions is divided into 5 levels of perceived problems (level 1 = no problem, level 2 = slight problems, level 3 = moderate problems, level 4 = severe problems, level 5 = extreme problems). The participant selects an answer for each of the 5 dimensions considering the response that best matches his or her health "today." The descriptive system can be represented as a health state. Individual scores from the 5 dimensions will be used to obtain a weighted health status index as follows:

- Scores from each dimension will be combined to obtain a 5L health state: e.g., a score of 1 for each dimension will give a 5L health state of 11111. Dimension scores will be combined in the following order: Mobility, Self-Care, Usual Activities, Pain/Discomfort, Anxiety/Depression;
- ii) The EuroQol Group coordinated a study that administered both the 3-level and 5-level versions of the EQ-5D, in order to develop a "crosswalk" between the EQ-5D-3L value sets and the new EQ-5D-5L descriptive system, resulting in crosswalk value sets for the EQ-5D-5L.

Interim Scoring for the EQ-5D-5L: Mapping the EQ-5D-5L to EQ-5D-3L Value Sets (Van Hout et al, 2012);

iii) The UK value set will be used to get the health utility values for all the countries participating in the study. See "*EQ-5D-5L_Crosswalk_Value_Sets.xls*".

The EQ-VAS self-rating records the respondent's own assessment of his or her overall health status at the time of completion, on a scale of 0 to 100.

Analysis Methods

See section 5.5.1 for the analysis of the EQ-Health-Utility and the EQ-VAS.

Frequency distributions will be provided for the 5 dimensions of the EQ-5D-5L descriptive system for each scheduled visit. Summaries of both observed and LOCF data will be presented.

5.5.11. 36-Item Short-Form Health Survey (SF-36v2)

Definitions

The SF-36 is a validated 36-item questionnaire which measures quality of life across 8 domains, which are both physically and emotionally based. Version 2 of this questionnaire, with a 4-week recall (standard version) will be used for this study. The 8 domains that the SF-36 measures are as follows: physical functioning; role limitations due to physical health; role limitations due to emotional problems; energy/fatigue; emotional wellbeing; social functioning; pain; general health. In addition to the 8 scales two summary scales are calculated, the physical component summary scale (PCS) and the mental component summary scale (MCS). A single item (item 2) is also included that identifies perceived change in health, "Compared to one year ago, how would you rate your health in general now?".

Individual items will be scored on a 3-point, 5-point or 6-point scale. To construct the 8 dimensions, items will be recoded, the item values will be summed and transformed to a score of 0 to 100, where 100 indicates the best possible answer and 0 the worst possible answer. Finally, a

Dimension	Item	Abbreviated Item Content	Precoded	Final value
Physical Functioning (PF)	3a 3b 3c 3d 3e 3f 3g 3h 3i 3j	Vigorous activities, such as running, lifting heavy objects, or participating in strenuous sports Moderate activities, such as moving a table, pushing a vacuum cleaner, bowling, or playing golf Lifting or carrying groceries Climbing several flights of stairs Climbing one flight of stairs Bending, kneeling, or stooping Walking more than a mile Walking several hundred yards Walking one hundred yards Bathing or dressing oneself	1, 2, 3	1, 2, 3
Role- Physical (RP)	4a 4b 4c 4d	Cut down the amount of time one spent on work or other activities Accomplished less than you would like Limited in kind of work or other activities Had difficulty performing work or other activities (e.g., it took extra effort)	1, 2, 3, 4, 5	1, 2, 3, 4, 5
Bodily Pain	7	Intensity of bodily pain	1, 2, 3, 4, 5, 6	6.0, 5.4, 4.2, 3.1, 2.2,
	8	Extent pain interfered with normal work	If item 7 is not answered: 1, 2, 3, 4, 5 If item 7 is answered as 1 and item 8 as 1 If item 7 is answered as 2-6 and item 8 as 1 If item 7 is answered as 1-6 and item 8 as: 2, 3, 4, 5	 6.0, 4.75, 3.5, 2.25, 6 5 4. 3. 2. 1
General Health (GH)	1 11a 11b 11c 11d	Is your health: excellent, very good, good, fair, poor Seem to get sick a little easier than other people As healthy as anybody I know Expect my health to get worse Health is excellent	1, 2, 3, 4, 5 1, 2, 3, 4, 5	5.0, 4.4, 3.4, 2.0, 1.0 1, 2, 3, 4, 5 5, 4, 3, 2, 1 1, 2, 3, 4, 5 5, 4, 3, 2, 1
Vitality (VT)	9a 9e 9g 9i	Feel full of life Have a lot of energy Feel worn out Feel tired	1, 2, 3, 4, 5 1, 2, 3, 4, 5 1, 2, 3, 4, 5 1, 2, 3, 4, 5 1, 2, 3, 4, 5	5, 4, 3, 2, 1 5, 4, 3, 2, 1 1, 2, 3, 4, 5 1, 2, 3, 4, 5
Social Functioning (SF)	6 10	Extent health problems interfered with normal social activities Frequency health problems interfered with social	1, 2, 3, 4, 5 1, 2, 3, 4, 5	5, 4, 3, 2, 1 1, 2, 3, 4, 5
Role- Emotional (RE)	5a 5b 5c	Cut down the amount of time spent on work or other activities Accomplished less than you would like Did work or other activities less carefully than usual	1, 2, 3, 4, 5	1, 2, 3, 4, 5

norm-based score will be calculating. See the following table that defines the domains and the item recoding.

Dimension	Item	Abbreviated Item Content	Precoded	Final value
Mental Health (MH)	9b 9c 9d 9f 9h	Been very nervous Felt so down in the dumps that nothing could cheer you up Felt calm and peaceful Felt downhearted and depressed	1, 2, 3, 4, 5 1, 2, 3, 4, 5	1, 2, 3, 4, 5 1, 2, 3, 4, 5 5, 4, 3, 2, 1 1, 2, 3, 4, 5 5, 4, 3, 2, 1
Reported	2	How health is now compared to 1 year ago	1, 2, 3, 4, 5	1, 2, 3, 4, 5
An excerpt from the User's Manual for the SF-36v2 Health Survey				

Each raw scale score will be transformed to a 0 - 100 scale using the formula shown below and using the information of the following table:

Scale	Lowest possible raw score	Possible raw score range
Physical Functioning (PF)	10	20
Role-Physical (RP)	4	16
Bodily Pain (BP)	2	10
General Health (GH)	5	20
Vitality (VT)	4	16
Social Functioning (SF)	2	8
Role-Emotional (RE)	3	12
Mental Health (MH)	5	20

If PF is the raw score for the Physical Functioning scale, then:

PFtrans = 100 * (*PF* - "lowest possible raw score") / "possible raw score range"

For ease of interpretation the domain scores are converted to norm-based scores with mean=50 and SD=10, using the formulas (given for Physical Functioning scale):

PFz-score = ($PFtrans - mean_{PF}$) / SD_{PF} Norm-based PF = PFz * 10 + 50

The mean and SD to calculate the z-scores for the 8 scales are in the following table:

SF-36 scale	Mean	SD
PF	83.29094	23.75883
RP	82.50964	25.52028
BP	71.32527	23.66224
GH	70.84570	20.97821
VT	58.31411	20.01923
SF	84.30250	22.91921
RE	87.39733	21.43778
МН	74.98685	17.75604

(see: Ware JE, Kosinski M, Dewey JE. How to Score Version 2 of the SF-36® Health Survey. Lincoln, RI: QualityMetric Incorporated, 2000).

The physical component summary scale (PCS) and the mental component summary scale (MCS). are calculated as follows:

And then both scales will be converted to norm-based score in the same way as above.

Analysis Methods

See section 5.5.1 for the analysis of the norm-based scores of the 8 SF-36v2 dimensions and the two summary scores.

Frequency distributions will be provided for item 2 of the SF-36v2 for each scheduled visit. Summaries of both observed and LOCF data will be presented.

5.5.12. Sheehan Disability Scale (SDS)

Definitions

The SDS will be used to assess the secondary objective of functional impairment and associated disability. The SDS is a validated PRO measure consisting of a 5-item questionnaire that has been widely used and accepted for assessment of functional impairment and associated disability. The first 3 items assess disruption of (1) work/school, (2) social life, and (3) family life/home responsibilities using a rating scale from 0 to 10. The SDS also has 1 item assessing days lost from school or work and 1 item assessing days of underproductivity. The recall period for this study is 7 days. The first item (work/school) may be missing due to not working/studying unrelated to the disease.

The scores for the first 3 items are summed to create a total score of 0 to 30, where higher score indicates greater impairment. Scores ≤ 2 for each item and ≤ 6 for the total score are considered functional remission. If one of the first three items is missing, the total score will be calculated by imputing the missing item with the average of the other two items. Otherwise the total score will be set to missing as well as remission status.

Analysis Methods

See section 5.5.1 for the analysis of the SDS total score and the days lost items.

Frequency distributions will be provided for the SDS remission for each scheduled visit. Summaries of both observed and LOCF data will be presented.

5.5.13. Work Productivity and Activity Impairment (WPAI-D)

Definitions

The WPAI:D questionnaire is a validated short instrument that assesses impairment in work and other regular activities over the past 7 days. The WPAI yields four types of scores:

- 1. Absenteeism (work time missed)
- 2. Presenteeism (impairment at work / reduced on-the-job effectiveness)

- 3. Work productivity loss (overall work impairment / absenteeism plus presenteeism)
- 4. Activity Impairment.

The first three scores will be derived only for respondents who are working (should be missing for non-working), but the last score is applicable for all respondents. WPAI scores are expressed as percent impairment, with higher values indicating greater impairment. A score cannot be calculated if there is a missing response to the corresponding item.

The questions of the WPAI-D are:

Q1 = currently employed

- Q2 = hours missed due to problems associated with depression
- Q3 = hours missed other reasons
- Q4 = hours actually worked
- Q5 = degree depression affected productivity while working
- Q6 = degree depression affected regular activities

The 4 scores are calculated as follows:

- 1. Absenteeism: Q2*100/(Q2+Q4)
- 2. Presenteeism: Q5*10
- 3. Work productivity loss: 100*[Q2/(Q2+Q4) + (1 Q2/(Q2+Q4)) * Q5/10]
- 4. Activity Impairment: Q6*10

Analysis Methods

See section 5.5.1 for the analysis of the 4 WPAI scores.

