Clinician-rated depressive symptoms	• Clinician-rated overall severity of depressive illness:	
	 Clinical Global Impression – Severity (CGI-S) 	
	 Clinical Global Impression – Change (CGI-C), is a measure of change, analyzed as a score not as change from baseline 	
Participant-reported depressive symptoms	• Participant-reported depressive symptoms: Patient Health Questionnaire 9-item (PHQ-9)	
and associated disability	• Participant-reported functional impairment	
 Participant-reported health-related quality of life and health status Participant-reported work productivity 	and associated disability: Sheehan Disabili Scale (SDS)	
	• Participant-reported health-related quality of life and health status: 36-item Short-Form Health Survey (SF-36)	
	• Participant-reported Quality of Life in Depression Scale (QLDS)	
	• Participant-reported European Quality of Life (EuroQoL) Group, 5-Dimension, 5-Level (EQ-5D-5L) questionnaire	
	• Participant-reported work productivity: Work Productivity and Activity Impairment (WPAI): Depression (D) questionnaire	

Objectives	Endpoints
To assess the safety and tolerability of esketamine nasal spray compared with quetiapine XR, both in combination with a continuing SSRI/SNRI.	Intervention-emergent adverse events (AEs), including intervention-emergent AEs of special interest
	Suicidal ideation and behavior: Columbia-Suicide Severity Rating Scale (C-SSRS)
Exploratory	
To assess the potential relationship of biomarkers with response/nonresponse to study intervention in participants with treatment-resistant MDD.	-

Refer to Section 8, Study Assessments and Procedures for evaluations related to endpoints.

HYPOTHESES

The primary and secondary hypotheses are provided in Section 9.1, Statistical Hypotheses.

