5.5. Supportive Secondary Endpoint(s)

5.5.1. General Analysis Methods

For continuous/ordinal parameters (eg, MADRS, CGI-S, PHQ-9, EQ-5D-5L, SF-36, SDS, WPAI:D) descriptive statistics of the score or values and change from baseline will be provided for each study visit during the study for the full analysis set. For CGI-C descriptive statistics of the score will be provided for each study visit during the study by study intervention for the full analysis set. Summaries of both observed and last observation carried forward (LOCF) data will be presented. The change from baseline at each visit will be analyzed using a mixed model for repeated measurements based on observed cases. The model will include baseline score as a covariate, and study intervention, stratification factors (age [18 to 64 years (inclusive); 65 to 74 years (inclusive)] and total number of treatment failures [2; 3 or more]), visit, and visit-by-study intervention interaction as fixed effects applying an unstructured covariance matrix. In case of issue with convergence of the model, alternative structures of variance-covariance matrix will be tested. The change from baseline at each visit will also be analyzed using an analysis of covariance model including LOCF data with factors for treatment, stratifications factors (age [18 to 64 years

(inclusive); 65 to 74 years (inclusive)] and total number of treatment failures [2; 3 or more]) and baseline score as a covariate. For all model approaches, LS estimates of the treatment differences at each visit and 95% confidence intervals will be presented. Additionally, for the MMRM model, the LS mean change from baseline averaged over all visits will be presented with 95% confidence interval per treatment group. The corresponding treatment difference will be presented with 95% confidence interval and two-sided p-value.

Additionally, for scales that have a minimum clinically important difference (MCID), the proportion of participants having improved by at least the MCID will be described at each visit and compared between study interventions using CMH chi-square test adjusting for age (18 to 64 years [inclusive]; 65 to 74 years [inclusive]) and total number of treatment failures (2; 3 or more). The same analysis will be conducted for the proportion of participants who deteriorate by at least the MCID.

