6.3. Appendix 3 Demographics and Baseline Characteristics

6.3.1. Demographics

The following demographic variables will be summarized by intervention group:

Continuous Variables	Summary Type
Age (years)	Descriptive statistics (N, mean, standard deviation [SD], median and range [minimum and maximum]
Weight (kg) at baseline	
Categorical Variables	
Age (18-64 years, >=65 years)	
Sex (male, female, undifferentiated)	
Japanese Ancestry (Yes, No)	
Occupational/employment status (full time employed, part time employed, casually employed, sheltered work, employed, but currently on sick or disability leave, unemployed due to depression, but seeking work, unemployed for reasons unrelated to depression, but seeking work, unemployed due to depression, but not seeking work, unemployed for reasons unrelated to depression, but not seeking work, retired, housewife or dependent husband/partner, student, no information available)	Frequency distribution with the number and percentage of participants in each category.

The following variables will be summarized for female participants by intervention group:

Continuous Variables	Summary Type	
Average length of menstrual cycle (days)	Descriptive statistics (N, mean, standard deviation	
Time from last menstrual period to date of assessment	[SD], median and range [minimum and maximum]	
Categorical Variables		
Subject's childbearing potential (of childbearing potential, permanently sterilized, postmenopausal, not applicable)	Frequency distribution with the number and percentage of participants in each category.	
Did menstrual period occur since last assessment (Yes, No)		

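### As written, SAP 5.5.13 and 5.5.1 together carry WPAI work scores forward by LOCF into visits at which a participant is no longer employed

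*SAP*

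**What the plan says.** Work productivity is one of the other secondary endpoints in Protocol section 3: "Participant-reported work productivity: Work Productivity and Activity Impairment (WPAI): Depression (D) questionnaire".

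SAP 5.5.13 defines four WPAI scores. Three of them (absenteeism, presenteeism, work productivity loss) exist only for people in work: "The first three scores will be derived only for respondents who are working (should be missing for non-working". The fourth, Activity Impairment, applies to everyone. The section closes with an unqualified cross-reference: "See section 5.5.1 for the analysis of the 4 WPAI scores".

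SAP 5.5.1 covers the scale by name: "For continuous/ordinal parameters (eg, MADRS, CGI-S, PHQ-9, EQ-5D-5L, SF-36, SDS, WPAI:D) descriptive statistics of the score or values and change from baseline". For the parameters it lists it plans:

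- descriptive summaries in two versions: "Summaries of both observed and last observation carried forward (LOCF) data will be presented";
- a mixed model without carried values: "The change from baseline at each visit will be analyzed using a mixed model for repeated measurements based on observed cases";
- a second model with carried values: "The change from baseline at each visit will also be analyzed using an analysis of covariance model including LOCF data".

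Protocol 9.4.2 contains the same rules and also names WPAI:D. SAP Appendix 2 (changes to protocol-planned analyses) records no departure for WPAI.

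**The concern.** A work score can be absent for two different reasons. Either the questionnaire was not completed, or it was completed and the respondent said that he or she was not employed. In the second case nothing is unobserved: the score is undefined, as SAP 5.5.13 itself says. A LOCF rule that does not separate the two cases fills both.

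The second case matters because leaving work can be a consequence of the disease. The SAP's own baseline employment categories (6.3.1) include "unemployed due to depression, but seeking work". A participant who improves somewhat, then loses the job, would be shown at every later visit with the work score from the last visit in employment. The LOCF tables would then report work impairment for people without work, and the apparent number of workers at late visits would be too high. If leaving work differs between arms, the LOCF treatment difference for these three scores would be shifted.

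**Working it through.** The documents give no WPAI figure to reproduce, so the check has three steps: the texts side by side, one hypothetical participant, and a scale calculation on assumed rates.

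**1. The texts.** SAP 5.5.13 makes scores 1-3 missing when the respondent is not working, and sends those same scores to SAP 5.5.1. SAP 5.5.1 applies LOCF at each visit and has no clause for a score that is undefined. Neither section says which governs. The SAP does restrict LOCF elsewhere: for a missing Week 8 MADRS (5.3.2 and 5.4.1.2) it is limited to participants who neither discontinued study intervention nor withdrew before Week 8. No restriction of any kind is given for WPAI.

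**2. One participant, with the SAP 5.5.13 formulas.** Absenteeism = 100 × Q2/(Q2+Q4). Presenteeism = 10 × Q5. Work productivity loss = 100 × [Q2/(Q2+Q4) + (1 − Q2/(Q2+Q4)) × Q5/10]. The answers below are invented for illustration.

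| Visit | Q2 | Q4 | Q5 | Absenteeism | Presenteeism | Work productivity loss |
|---|---|---|---|---|---|---|
| Day 1 | 16 | 24 | 8 | 40% | 80% | 100 × (0.40 + 0.60 × 0.8) = 88% |
| Week 4 | 12 | 28 | 6 | 30% | 60% | 100 × (0.30 + 0.70 × 0.6) = 72% |
| Week 8 | 8 | 32 | 5 | 20% | 50% | 100 × (0.20 + 0.80 × 0.5) = 60% |
| Week 12 on | not employed | | | undefined | undefined | undefined |

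- Observed cases: no work score at Weeks 12, 16, 20, 24, 28 and 32.
- LOCF as written: 20%, 50% and 60% are entered at all six visits. The ANCOVA counts a change of 60 − 88 = −28 points, an improvement, for someone who no longer has a job.

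**3. Scale.** Inputs: 311 per arm (SAP section 3). The share working on Day 1 (30-70%) and the share of those who leave work (5-20%) are assumptions.

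- Carried values per arm at Week 32 = 311 × share working × share leaving.
- Low: 311 × 0.30 × 0.05 = 4.7, about 5.
- High: 311 × 0.70 × 0.20 = 43.5, about 44.

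Next, the effect on the arm difference. Let the carried scores of leavers differ on average by *g* points from the scores of those still working, in both arms, and let *f* be the share of leavers in an arm. The LOCF mean of the arm then differs from the mean among those still working by *g* × *f*, so the arm difference shifts by *g* × (*f*₁ − *f*₂). With *g* assumed to be 10-30 points, the absolute shifts are:

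| Leaving work | g = 10 | g = 20 | g = 30 |
|---|---|---|---|
| 10% vs 10% | 0 | 0 | 0 |
| 5% vs 10% | 0.5 | 1.0 | 1.5 |
| 5% vs 15% | 1.0 | 2.0 | 3.0 |

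The direction depends on which arm loses more workers and on whether carried scores lie above or below those of people still working. The documents settle neither.

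**The case against.** The strongest reply is that the SAP gives no LOCF algorithm for these scales, and that the specific sentence in 5.5.13 should override the general rule in 5.5.1. A careful programmer could leave the work score missing at any visit where Q1 is no, and carry values only when the questionnaire is absent. That reading is reasonable. However, no text instructs it, and two programmers could produce different LOCF tables from the same plan. So the defect is an unstated precedence whose literal reading gives the wrong result. It is not certain that the tables will be wrong.

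A reader might infer more than the documents support:

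- *That all WPAI analyses are affected.* The observed summaries and the observed-case MMRM carry nothing forward and already give no work score at a non-working visit. That they describe only people in work follows from how the scores are defined.
- *That the bias can be sized by treating a person who left work as 100% impaired.* The SAP formula gives 100% to an employed respondent whose hours were all lost to depression (Q2 above 0, Q4 equal to 0, Q5 answered). Neither the SAP nor the fix below assigns that value to someone without a job. The relevant contrast is a carried value against no value, as in step 3.
- *That values could be carried to all eight post-baseline WPAI visits.* This would require carrying the Day 1 value forward, which the SAP does not state. If only post-baseline values are carried, the maximum is seven.
- *That anyone returning to work has no change score.* This holds only for those not working on Day 1. They lack a baseline work score and stay out of the change analyses, but they enter the observed summaries of the score.
- *That the worst outcomes go unseen.* Activity Impairment is scored for all respondents, and the SDS (SAP 5.5.12) covers disruption of work or school and days lost.
- *That the lack of an employment-by-visit table is an error.* No objective or endpoint concerns change in employment status.

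**Conclusion.** The point holds for the LOCF summaries and the LOCF ANCOVA of absenteeism, presenteeism and work productivity loss. Read literally, they include work scores for people who have left work, against the definition in SAP 5.5.13. It does not extend to the other WPAI analyses, and it does not touch the primary or key secondary endpoint.

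The size cannot be taken from the documents. The ranges in step 3 rest entirely on assumed rates of employment and job loss and on an assumed score gap, taken as equal in the two arms. On those assumptions the arm difference moves by at most about 3 points, and not at all if leaving work is equally common in both arms. The severity is low: a real inconsistency in one of two model approaches for a supportive secondary scale, and easy to repair.

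**What to change.** Add to SAP 5.5.13 that LOCF is not applied to WPAI scores 1-3 at visits where Q1 (currently employed) is no, and that a value is carried forward only when the questionnaire itself is missing. It would help to say that this takes precedence over SAP 5.5.1.

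The cost is a sentence or two in the SAP, one condition in the derivation program, and smaller LOCF denominators for the three work scores. No new data are needed.

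Optionally, show the number employed (Q1) by visit and arm. This would let a reader see how many people each work score describes, but it is a matter of presentation and the correction does not depend on it.
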